#### 7.5 Interim Analyses and Data Monitoring

No formal interim analyses were planned nor carried out for this study. The study was overseen by a Data and Safety Monitoring Board (DSMB) that reviewed the subject disposition, study conduct and safety data throughout the trial.

#### 7.6 Multiple Testing

Statistical testing is conducted at the 0.05 significance level using two-tailed tests; two-sided p-values are reported. No adjustments for multiplicity are planned for this pilot study. Rather, inferences and decision-making are based primarily on the magnitude of treatment effects.

## 8. Summary of Study Conduct Data

Descriptive summary statistics are tabulated for baseline patient demographics and clinical characteristics (overall since this is a single-arm study). Continuous variables are summarized using descriptive statistics including n, mean, median, standard deviation, interquartile range (i.e., 1st and 3rd quartiles), and range (i.e., minimum and maximum). Qualitative variables will be summarized using counts and percentages. Unless otherwise specified, statistical analyses will be performed using SAS Version 9 or higher. Where appropriate, statistical tests will be conducted at the 0.05 significance level using two-tailed tests and p-values will be reported.

## 8.1 Subject Disposition

The number and percentage of participants consented, treated and withdrawn, along with reasons for withdrawal, are tabulated and summarized in a CONSORT diagram. Other disposition and study conduct information, including major protocol violations are summarized. Protocol deviations are provided in a listing. Duration of study follow-up is summarized.

## 8.2 Derived Variables

#### 8.2.1 eGFR

The formulas used to calculate eGFR in adults and children are given below:

CKID U25 age- and sex-dependent equation using serum creatinine (Pierce, 2021) [4]
 for patient whose age is younger than 25 years old:

```
eGFR = k × (height/serum creatinine), with height in meters and serum creatinine in mg/dL For males, k is calculated as:

For 1 to 11 years old: 39.0 \times 1.008^{(age-12)}

For 12 to 17 years old: 39.0 \times 1.045^{(age-12)}

For 18 to 25 years old: 50.8

For females, k is calculated as:

For 1 to 11 years old: 36.1 \times 1.008^{(age-12)}

For 12 to 17 years old: 36.1 \times 1.023^{(age-12)}

For 18 to 25 years old: 41.4
```

• CKD-EPI equation for patient whose age is greater than 25 years old [5]:

```
eGFRcr = 142 x min(Scr/κ, 1)α x max(Scr/κ, 1)-1.200 x 0.9938Age x 1.012 [if female] where: Scr = standardized serum creatinine in mg/dL  \kappa = 0.7 \text{ (females) or } 0.9 \text{ (males)}   \alpha = -0.241 \text{ (female) or } -0.302 \text{ (male)}  min(Scr/κ, 1) is the minimum of Scr/κ or 1.0 max(Scr/κ, 1) is the maximum of Scr/κ or 1.0 Age (years)
```

#### 8.2.2 Blood pressure index

The 2017 ACC/AHA hypertension guideline applied a lower threshold for defining hypertension and 130 (mmHg) /80 (mmHg) are the thresholds for hypertension in adult's guidelines. [6] An important update in the 2017 AAP CPG is a change in the definition of hypertension in children and adolescents: In children <13 years of age, hypertension is defined as systolic or

diastolic blood pressure ≥95th percentile on the new sex, age, and height tables. For adolescents ≥13 years of age, the 95th percentile approximates 130/80 mm Hg. Therefore, the 2017 AAP CPG has used the new adult blood pressure cut-points to define hypertension in adolescents ≥13 years of age. [7]

To allow for comparison across adults and children, systolic and diastolic blood pressure indices are calculated with the method below:

- For the patient whose age was 13 years or greater, the measured systolic blood pressure was divided by 130 (and the measured diastolic blood pressure was divided by 80)
- For the patient whose age was younger than 13 years, the measured systolic and the measured diastolic blood pressure were divided by the sex, age, and height specific 95th percentile systolic and diastolic blood pressure, respectively [8]

We use the Childhood Blood Pressure Macro-batch mode to calculate the specific  $95^{th}$  percentile blood pressure of the patient whose age is younger than 13 years. [9][10] Then the blood pressure index is calculated based on the method above. Blood pressure index  $\geqslant 1$  indicates blood pressure in the hypertensive range and every 0.1-unit increase represents a 10% increase in blood pressure above the hypertensive range.

## 8.2.3 Laboratory abnormality variables

Elevation of ALT, AST or total bilirubin of > 2x ULN were prespecified as events of interest and were coded as 1 for values  $\ge 2x$  ULN, 0 for values below 2 x ULN. These are calculated for each participant at each time point.

Abnormal low values for hemoglobin, hematocrit, and platelet count were specified as events of interest and were coded as 1 for values < age-matched LLN and 0 otherwise. Abnormal high values for hemoglobin, hematocrit, and platelet counter were also specified as events of interested and were coded 1 for values > age-matched ULN and 0 otherwise. Any laboratory abnormality for these laboratory parameters were coded as 1 if abnormally low or high and 0 otherwise. These are calculated for each participant at each time point.

#### 8.3 Demographic and Baseline Variables

Demographic and baseline variables for participants include: age in years at baseline, sex (male/female), ethnicity (Hispanic or Latino/not Hispanic or Latino/refused/missing), race (White/Black or African American/Asian/American Indian or Alaskan native/native Hawaiian or other Pacific Islander/refused/missing), duration of kidney disease (in months), baseline medication use (%), weight (kg), edema/no edema status, blood pressure index, eGFR (mL/min/1.73 m²), UPCR (mg/mg), albumin (g/dL), hemoglobin (g/dL), WBC (k/mm³), cholesterol (mg/dL), AST (U/L), ALT (U/L), total bilirubin (mg/dL), hematocrit (%), platelet count (K/uL), urinary MCP/uCr (ng/mg), urinary TIMP1/uCr (ng/mg), uEGF/uCr (ng/mg), PRO Score, and TNF activation score.

## 8.4 Treatment Compliance

Compliance with study medication is summarized as the proportion of participants who received 1, 2, 3, 4, and (all) 5 doses of adalimumab. Descriptive statistics on the duration of adherence to study medication is summarized. The proportion of participants who permanently discontinue study medication is summarized with descriptive statistics and a listing provided of these participants with their reasons for permanent discontinuation of study medication.

## 9. Statistical Methods

## 9.1 Analyses of Primary Endpoints

The changes in urinary MCP1/uCr and urinary TIMP1/uCr levels from baseline to study week 10, i.e., 2 weeks after the final dose of adalimumab, are the primary endpoints. We provide tabular and graphical summaries of the changes from baseline to week 10 in urinary MCP1/uCr and in urinary TIMP1/uCr, including summaries at baseline and week 10. The changes from baseline to week 10 in urinary MCP1/uCr and urinary TIMP1/uCr levels will be tested using the Wilcoxon signed-rank test.

## 9.2 Analyses of Secondary Endpoints

Discrete safety outcomes (AEs, SAEs, AEs leading to premature discontinuation of study medication, and proportion of participants with abnormal laboratory tests, fever and new or worsening edema compared with baseline over the course of the 10-week treatment period) and discrete preliminary efficacy outcomes (proportion of participants achieving a nadir UPCR <1.5 g/g and at least a 40% reduction from baseline at week 10) are summarized descriptively.

Percent change in eGFR from baseline to week 10 and percent change in UPCR from baseline to week 10 are summarized descriptively in tabular and graphical formats, including baseline, follow-up and changes from baseline. Graphical summaries include spaghetti plots of participants' changes over time.

Clinical laboratory tests as described in Section 6.2.2 are summarized descriptively in tables and graphically with individual plots of laboratory value by visit with a reference line for LLN, ULN and 2xULN for those participants who have at least one abnormal value during the course of the study. A shift table (normal and abnormal results for screening and post-treatment values at each time point) for each clinical laboratory test of interest will be presented.

For discrete safety outcomes, frequency of events and proportion of participants experiencing events (i.e., treatment-emergent AEs and SAEs by body system, severity, and relatedness to adalimumab) will be summarized descriptively.

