Use of TNF blockers, including Humira, may increase the risk of reactivation of hepatitis B virus (HBV) in patients who are chronic carriers. Some cases have been fatal. Study participants will be screened for HBV. Those with prior evidence of HBV infection will not be allowed to participate in this study.

NEUROLOGIC REACTIONS

TNF blockers, including Humira, have been associated with rare cases of new onset or exacerbation of central nervous system and peripheral demyelinating diseases, including multiple sclerosis, optic neuritis, and Guillain-Barré syndrome. Participants with these disorders will be excluded from the study. If any of these disorders develop, Humira will be discontinued.

HEMATOLOGIC REACTIONS

Rare reports of pancytopenia, including aplastic anemia, have been reported with TNF blockers. Medically significant cytopenia has been infrequently reported with Humira.

CONGESTIVE HEART FAILURE

Worsening and new onset congestive heart failure (CHF) has been reported with TNF blockers. Cases of worsening CHF have been observed with Humira. Participants with known CHF will be excluded from the study.

AUTOIMMUNITY

Treatment with Humira may result in the formation of autoantibodies and, rarely, in development of a lupus-like syndrome. Discontinue treatment if symptoms of a lupus-like syndrome develop.

IMMUNIZATIONS

Patients on Humira should not receive live vaccines. Pediatric patients, if possible, should be brought up to date with all immunizations before initiating Humira therapy. Adalimumab is actively transferred across the placenta during the third trimester of pregnancy and may affect immune response in the in utero exposed infant. The safety of administering live or live-attenuated vaccines in infants exposed to Humira in utero is unknown. Risks and benefits should be considered prior to vaccinating (live or live-attenuated) exposed infants.

ADVERSE REACTIONS

The most common adverse reactions in Humira clinical trials (>10%) were: infections (e.g., upper respiratory, sinusitis), injection site reactions, headache, and rash.

Directly relevant to this protocol, two small studies of TNF-inhibition with monoclonal antibody therapy in children and adults with multi-drug resistant FSGS have been reported.

•	•
Event	Frequency (% of patients reporting)
Severe Adverse Events	
Infection with hospitalization	30% (5/17)
Malignancy	0
Death	0
Other Adverse Events	
GI	24% (4/17)

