## 4.2 Secondary Endpoints

- 1. Incidence of serious adverse events, defined as the proportion of participants with treatment-emergent serious adverse events and the number of treatment-emergent serious adverse events, overall, by system organ classification, by relatedness to study medication, and by severity
- 2. Incidence of non-serious adverse events, defined as the proportion of participants with treatment-emergent non-serious adverse events and the number of treatment-emergent non-serious adverse events, overall, by system organ classification, by relatedness to study medication, and by severity
- 3. Incidence of adverse events leading to premature discontinuation of study medication, defined as the proportion of participants with treatment-emergent adverse events and the number of treatment-emergent adverse events that led to premature discontinuation of study medication, overall, by system organ classification, by relatedness to study medication, and by severity
- 4. Proportion of participants with abnormal laboratory tests for ALT, AST, total bilirubin, hemoglobin, hematocrit, and platelet count, proportion of participants with temperature ≥38.5°C (indicating fever), and proportion of participants with any edema (over all body locations and by each location) over the course of the 10-week intervention period
- 5. Percent change in eGFR from baseline to week 10
- 6. Percent change in UPCR from baseline to week 10
- 7. Proportion of participants achieving a nadir UPCR less than 1.5 g/g and at least a 40% reduction from baseline at week 10

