#### 6.2.2 Laboratory abnormalities

For ALT, AST, and total bilirubin, the laboratory result value is abnormal when it is greater than 2 x upper limit of normal (ULN). Laboratory result values either below the age-matched lower limit of normal (LLN) or above the age-matched upper limit of normal is defined as laboratory abnormalities for hemoglobin, hematocrit, and platelet count. The age-matched normal ranges of ALT, AST, total bilirubin, hemoglobin, hematocrit, and platelet count are provided below:

	Age Group	Male	Female
ALT	> or =6 year	7-55 U/L	7-45 U/L
AST	6-13 years	8-60 U/L	8-50 U/L
	> or =14 years	8-48 U/L	8-43 U/L
Total bilirubin	6 to 17 years	0.0-1.0 mg/dL	0.0-1.0 mg/dL
Hemoglobin	6-8 years	11.5-14.3 g/dL	11.5-14.3 g/dL
	9-10 years	11.8-14.7 g/dL	11.8-14.7 g/dL
	11-14 years	12.4-15.7 g/dL	11.9-14.8 g/dL
	15-17 years	13.3-16.9 g/dL	11.9-14.8 g/dL
	Adults	13.2-16.6 g/dL	11.6-15.0 g/dL
Hematocrit	6-7 years	34-42%	34-42%
	8-11 years	35-43%	35-43%
	12-15 years	38-47%	35-43%
	16-17 years	40-50%	35-43%
	Adults	38.3-48.6%	35.5-44.9%
Platelet count	6-9 years	187-400 x 10  /L	187-400 x 10  /L
	10-13 years	177-381 x 10  /L	177-381 x 10  /L
	14-17 years	139-320 x 10  /L	158-362 x 10  /L
	Adults	135-317 x 10  /L	157-371 x 10  /L

We calculate the proportion of participants with laboratory abnormalities at weeks 2, 4, 8 and 10, and overall (i.e., a participant experienced a lab abnormality at any visit).

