- Table 17. Proportion of participants achieving a nadir UPCR <1.5 g/g and at least a 40% reduction from baseline at week 10. As-Treated Population.
- Table 18.1. Proportion of Participants with Abnormal Laboratory Tests for ALT, AST, Total Bilirubin, Hemoglobin, Hematocrit, and Platelet Count Over the Course of the 10-Week Intervention Period. As-Treated Population.
- Table 18.2. Shift Table for Normal and Abnormal Laboratory Test Changes from Screening to Weeks 0, 2, 8, 10, and 14 in ALT, AST, Total Bilirubin, Hemoglobin, Hematocrit, and Platelet Count. As-Treated Population.
- Table 19. Correlations between TNF activation score and urinary MCP1/uCr and TIMP1/uCr biomarker levels at baseline. As-Treated Population with Kidney Biopsy Tissue Collected within 12 Months of Study Baseline.

- Table 20.1. Change from baseline to weeks 2, 4, and 8 in urinary MCP1/uCr. As-Treated Population.
- Table 20.2. Percent change from baseline to weeks 2, 4, 8, and 10 in urinary MCP1/uCr. As-Treated Population.
- Table 20.3. Urinary MCP1/uCr values at baseline and weeks 2, 4, 8, and 10. As-Treated Population.
- Table 21.1. Change from baseline to weeks 2, 4, and 8 in urinary TIMP1/uCr. As-Treated Population.
- Table 21.2. Percent change from baseline to weeks 2, 4, 8, and 10 in urinary TIMP1/uCr. As-Treated Population.
- Table 21.3. Urinary TIMP1/uCr values at baseline and weeks 2, 4, 8, and 10. As-Treated Population.
- Table 22. Change in uEGF/uCr levels from baseline to weeks 2, 4, 8, and 10. As-Treated Population.
- Table 23. Correlation coefficient between uEGF/uCr at baseline with changes and percent changes in urinary MCP1/uCr and urinary TIMP1/uCr biomarker levels and in eGFR and UPCR values at week 10. As-Treated Population.
- Table 24. Changes in FSGS-MCD Patient Reported Outcome (PRO) score from baseline to weeks 2, 4, 8 and 10. As-Treated Population.

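### The SAP derives separate low and high codes for hemoglobin, hematocrit and platelets, but its two-level shift table drops the direction, so a new low reads the same as a new high

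*SAP*

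**What the plan says.** **The named harm.** Protocol 2.3.1, under hematologic reactions, states: "Rare reports of pancytopenia, including aplastic anemia, have been reported with TNF blockers". It adds: "Medically significant cytopenia has been infrequently reported with Humira". The prescribing highlights in Appendix A carry a cytopenia warning as well. All of these are falls.

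**The definition.** Under SAP 6.2.2, a hemoglobin, hematocrit or platelet result is abnormal if it is "either below the age-matched lower limit of normal (LLN) or above the age-matched upper limit of normal". ALT, AST and total bilirubin are judged on the upper side only.

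**The derived variables.** SAP 8.2.3 keeps the two directions apart: "Abnormal low values for hemoglobin, hematocrit, and platelet count were specified as events of interest". It treats high values in the same way and adds a third code for either direction. All are calculated for each participant at each time point.

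**The reporting.** SAP 4.2, item 4, is the "Proportion of participants with abnormal laboratory tests for ALT, AST, total bilirubin, hemoglobin, hematocrit, and platelet count" over the intervention period. It states no direction, and the title of Table 18.1 repeats it. On shifts, SAP 9.2 reads: "A shift table (normal and abnormal results for screening and post-treatment values at each time point) for each clinical laboratory test of interest will be" produced. Table 18.2 in SAP 12.1 is the "Shift Table for Normal and Abnormal Laboratory Test Changes from Screening to Weeks 0, 2, 8, 10, and 14". SAP 9.2 also plans individual plots by visit with lines at the lower and upper limits of normal, for participants with at least one abnormal value. Figures 6.4 to 6.6 are these plots for the three hematology tests.

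**The concern.** The SAP treats direction as important when it derives the variables and then leaves it out of the shift table. A two-level shift is adequate for the liver tests, where abnormal has one meaning. For the three hematology tests abnormal has two opposite meanings, and only one of them is the harm that the protocol names.

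A reader who turns to Table 18.2 to ask whether counts fell on treatment will not find the answer there. The listings in SAP 12.2 include no laboratory listing, so among tabulated output only adverse event reporting, which depends on the investigator's judgment, would speak to direction.

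**Working it through.** The plan states no figure on this point, so there is none to reproduce. The check is one of classification.

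**1. Transitions.** With low (L), normal (N) and high (H) at screening and again at a later visit there are 3 × 3 = 9 transitions. With normal and abnormal there are 2 × 2 = 4 cells, which merge the nine as follows:

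- normal to normal: N–N (1)
- normal to abnormal: N–L, N–H (2)
- abnormal to normal: L–N, H–N (2)
- abnormal to abnormal: L–L, L–H, H–L, H–H (4)

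The total is 1 + 2 + 2 + 4 = 9.

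**2. Examples against the SAP's own limits.** The adult ranges come from SAP 6.2.2: platelets 135–317 (male) and 157–371 (female) × 10⁹/L; hemoglobin 13.2–16.6 g/dL (male). The patient values are invented for illustration.

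| Test | Screening → later | Three-level | Two-level (SAP 9.2, Table 18.2) |
|---|---|---|---|
| Platelets, male | 250 → 120 | normal → low | normal → abnormal |
| Platelets, male | 250 → 330 | normal → high | normal → abnormal |
| Platelets, male | 330 → 120 | high → low | abnormal → abnormal |
| Platelets, female | 400 → 120 | high → low | abnormal → abnormal |
| Hemoglobin, male | 14 → 12 | normal → low | normal → abnormal |
| Hemoglobin, male | 14 → 17 | normal → high | normal → abnormal |
| Hemoglobin, male | 17 → 12 | high → low | abnormal → abnormal |
| Hemoglobin, male | 10 → 7.5 | low → low | abnormal → abnormal |

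In the first two rows, opposite changes share a cell. In the high-to-low rows, a fall across the whole normal range shows as no shift. The last row is a limit of the remedy: a low value that falls further stays in one cell under either scheme.

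**3. Can these patterns occur?** Exclusion criterion 16 sets lower bounds at enrollment (hemoglobin 9 g/dL, platelets 150,000/mm³) and no upper bounds, so a high screening value is possible. The documents give no basis for saying how likely it is. The shared normal-to-abnormal cell is the more practical problem, because it needs only a normal screening value.

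**4. Can a participant be low before dosing?** Yes. Entry allows hemoglobin from 9 g/dL, and the smallest lower limit in the SAP's hemoglobin table is 11.5 g/dL (ages 6–8). For platelets, entry allows 150 × 10⁹/L, and the adult female lower limit is 157. A low code on treatment is therefore not by itself a new event.

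**5. Weight of one participant.** With eight treated, one participant is 1/8 = 12.5 percentage points of a reported proportion. With six it is 1/6 = 16.7 points.

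**The case against.** The strongest reply is that the report will show direction anyway. The planned plots cover every participant with at least one abnormal value, at most eight people, against both limits. A participant who went from high to low must appear there, and is also counted as abnormal in Table 18.1. Clinically significant laboratory changes can be recorded as adverse events under Protocol 8.1.1, and those are tabulated and listed. All of this stands, and it is why the point is minor.

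It is also fair that SAP 12 places the tables in a separate file. Titles do not list rows, so Table 18.1 may already split low from high. For that table the most one can say is that the SAP text does not require it. The two-level shift is different, because SAP 9.2 states it as a rule.

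A reader might infer more than the documents support:

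- *That the SAP relies on a single two-sided flag.* It does not; 8.2.3 derives low, high and either.
- *That endpoint 4 misstates a cytopenia rate.* Protocol 4.2.2 and SAP 4.2 promise the incidence of abnormal tests, and neither calls it a cytopenia rate.
- *That high values are mere noise.* SAP 8.2.3 makes them events of interest too.
- *That one can calculate how many flags arise by chance on each side.* That would need the limits to be central 95% ranges and a participant's visits to be independent. The documents state neither.

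**Conclusion.** The point holds as a minor reporting gap. For hemoglobin, hematocrit and platelets, the shift specified in SAP 9.2 and Table 18.2 cannot separate a new low from a new high and shows a high-to-low fall as unchanged, although the named harm is a fall and the codes needed to show it already exist. For endpoint 4 and Table 18.1 the finding is narrower: no direction is stated, and the rows cannot be seen.

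The conclusion about the shift table rests only on the SAP's wording. The patient values above illustrate it and do not predict what will occur. Nothing here touches the primary analysis, the type I error or the sample size. The laboratory summaries are descriptive, and Protocol 8.5 defines no halting rules, so this is a matter of table layout and not of clinical management.

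**What to change.** - **SAP 9.2 and Table 18.2:** make the shift low/normal/high for hemoglobin, hematocrit and platelet count. Leave ALT, AST and total bilirubin at two levels.
- **Table 18.1 (and SAP 4.2, item 4):** state that the low and high codes from 8.2.3 appear on separate rows for these three tests, beside the pooled proportion.
- **Labeling:** call the row the proportion below the lower limit of normal, not a cytopenia rate. Add a note that it is to be read with the screening category in Table 18.2, because some participants may be low before the first dose.

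The cost is a few words of SAP text, two table shells and a few more rows; no new variable is needed. If the SAP can no longer be changed, a supplementary table would serve. Two limits remain. A low value that falls further will still show only in the plots, and white cells, which are collected in the blood count, are outside endpoint 4 and are not brought in by this change.
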